10.8. Appendix 8: Abbreviations and Definitions

Term	Definition
Aβ	amyloid beta
abuse	Use of a study intervention for recreational purposes or to maintain an addiction or dependence
AD	Alzheimer's disease
ADA	anti-drug antibody
AE	adverse event
ALP	alkaline phosphatase
ALT	alanine aminotransferase
ApoE4	apolipoprotein E genotype ε4
ARIA	amyloid-related imaging abnormalities
ARIA-E	ARIA–edema/effusions
ARIA-H	ARIA–hemorrhage/hemosiderin deposition
AST	aspartate aminotransferase
AUC_{0-4Weeks}	area under the concentration versus time curve 0 to 4 weeks
AUC_{0-∞}	area under the concentration versus time curve from time 0 to infinity
AUC_{0-t_{last}}	area under the concentration versus time curve from time 0 to last measured concentration
AUC_{τ,ss}	area under the concentration versus time curve during a dosing interval at steady state
BMI	body mass index
CDC	Centers for Disease Control and Prevention
C_{max}	maximum observed drug concentration
C_{max,ss}	maximum observed drug concentration during a dosing interval at steady state
complaint	A complaint is any written, electronic, or oral communication that alleges deficiencies related to the identity, quality, purity, durability, reliability, safety or effectiveness, or performance of a drug or drug delivery system.
Compliance	Adherence to all study-related, good clinical practice (GCP), and applicable regulatory requirements.
COVID-19	coronavirus disease 2019

CRF	case report form; a printed, optical, or electronic document designed to record all of the protocol-required information to be reported to the sponsor for each trial participant.
CRP	clinical research physician: Individual responsible for the medical conduct of the study. Responsibilities of the CRP may be performed by a physician, clinical research scientist, global safety physician or other medical officer.
CRU	clinical research unit
C-SSRS	Columbia-Suicide Severity Rating Scale
ECG	electrocardiogram
enroll	The act of assigning a participant to a treatment. Participants who are enrolled in the study are those who have been assigned to a treatment.
Enter	Participants entered into a study are those who sign the informed consent form directly or through their legally acceptable representatives.
HBV	hepatitis B virus
HCV	hepatitis C virus
HIV	human immunodeficiency virus
iADRS	integrated Alzheimer's Disease Rating Scale
IB	Investigator's Brochure
ICF	informed consent form
ICH	International Council for Harmonisation
IEC	Independent Ethics Committee
Ig	immunoglobulin
IMP	Investigational Medicinal Product (see also "investigational product") A medicinal product which is being tested or used as a reference, including as a placebo, in a clinical trial.
informed consent	A process by which a participant voluntarily confirms their willingness to participate in a particular study, after having been informed of all aspects of the study that are relevant to the participant's decision to participate. Informed consent is documented by means of a written, signed and dated informed consent form.
INR	international normalized ratio
investigational product	A pharmaceutical form of an active ingredient or placebo being tested or used as a reference in a clinical trial, including products already on the market when used or assembled (formulated or packaged) in a way different from the authorized form, or marketed products used for an unauthorized indication, or marketed products used to gain further information about the authorized form. See also "IMP."

IRB	Institutional Review Board
IRR	infusion-related reactions
IV	intravenous
MCI	mild cognitive impairment
N3pG	pyroglutamate formation of the third amino acid
participant	Equivalent to CDISC term “subject”: an individual who participates in a clinical trial, either as recipient of an investigational medicinal product or as a control
PC	product complaint
PCR	polymerase chain reaction
PK	pharmacokinetics
PT-INR	prothrombin time-international normalized ratio
Q2W	every 2 weeks
Q4W	every 4 weeks
QTc	corrected QT interval
SAE	serious adverse event
SARS-CoV-2	severe acute respiratory syndrome coronavirus 2 of the genus Betacoronavirus
screen	The act of determining if an individual meets minimum requirements to become part of a pool of potential candidates for participation in a clinical study.
SIB	suicidal ideation and behavior
SoA	Schedule of Activities
TBL	total bilirubin level
TE-ADA	treatment-emergent anti-drug antibodies
TEAE	Treatment-emergent adverse event: An untoward medical occurrence that emerges during a defined treatment period, having been absent pretreatment, or worsens relative to the pretreatment state, and does not necessarily have to have a causal relationship with this treatment.
ULN	upper limit of normal

11. References

2. ABBREVIATIONS

Abbreviations pertain to the Statistical Analysis Plan (SAP) only (not the tables, figures and listings [TFLs]).

%AUC($t_{last}-\infty$)	Fraction of AUC(0- ∞) extrapolated
AE	Adverse event
ADA	Anti-drug antibody
AUC	Area under the concentration versus time curve
AUC _{0-4weeks}	Area under the concentration vs time curve from time 0 to 4weeks
AUC _{0-2weeks}	Area under the concentration vs time curve for first dosing interval
AUC τ,ss	Area under the concentration versus time curve during one dosing interval at steady state
AUC(0- ∞)	Area under the concentration versus time curve from time zero to infinity
AUC(0- t_{last})	Area under the concentration versus time curve from time zero to time t, where t is the last time point with a measurable concentration
BQL	Below the quantifiable lower limit of the assay
CL	Total body clearance of drug calculated after intravenous administration
CL _{ss}	Total body clearance of drug calculated at steady state after intravenous administration
C _{last}	Last quantifiable drug concentration
C _{max}	Maximum observed drug concentration
C _{max,ss}	Maximum observed drug concentration during a dosing interval at steady state
C _{min,ss}	Minimum observed drug concentration during a dosing interval at steady state
CRU	Clinical Research Unit
CSR	Clinical Study Report
CSSRS	Columbia Suicide Severity Rating Scale
CV	Coefficient of variation
DMP	Data Management Plan
ECG	Electrocardiogram
ICH	International Conference on Harmonisation
IV	Intravenous

IRR	Infusion related reactions
MedDRA	Medical Dictionary for Regulatory Activities
PK	Pharmacokinetic
Q2W	Every 2 weeks
RA _{AUC}	Accumulation ratio for AUC _{τ,ss} at steady state / AUC _{0-2weeks}
RA _{Cmax}	Accumulation ratio for C _{max,ss} at steady state / C _{max, day 1}
SAE	Serious adverse event
SAP	Statistical Analysis Plan
SD	Standard deviation
SOP	Standard Operating Procedure
TBL	Total bilirubin
TE-ADA	Treatment emergent antidrug antibodies
TEAE	Treatment emergent adverse event
TFLs	Tables, Figures, and Listings
t _{1/2}	Half-life associated with the terminal rate constant (λ_z) in non-compartmental analysis
t _{max}	Time of maximum observed drug concentration
V _{ss}	Volume of distribution at steady state following intravenous administration
V _z	Volume of distribution during the terminal phase

3. INTRODUCTION

This SAP has been developed after review of the Clinical Study Protocol (final version dated 12 December 2022).

This SAP describes the planned analysis of the safety, tolerability and pharmacokinetic (PK) data from this study. A detailed description of the planned TFLs to be presented in the clinical study report (CSR) is provided in the accompanying TFL shell document.

The intent of this document is to provide guidance for the statistical and PK analyses of data. In general, the analyses are based on information from the protocol, unless they have been modified by agreement with Eli Lilly and Company. A limited amount of information concerning this study (e.g., objectives, study design) is given to help the reader's interpretation. This SAP must be finalized prior to first participant visit. When the SAP and TFL shells are agreed upon and finalized, they will serve as the template for this study's CSR.

This SAP supersedes the statistical considerations identified in the protocol; where considerations are substantially different, they will be so identified. If additional analyses are required to supplement the planned analyses described in this SAP, they may be performed and will be identified in the CSR. Any substantial deviations from this SAP will be agreed upon with Eli Lilly and Company and identified in the CSR. Any minor deviations from the TFLs may not be documented in the CSR.

This SAP is written with consideration of the recommendations outlined in the International Conference on Harmonisation (ICH) E9 Guideline entitled Guidance for Industry: Statistical Principles for Clinical Trials¹ and the ICH E3 Guideline entitled Guidance for Industry: Structure and Content of Clinical Study Reports².

4. STUDY OBJECTIVES AND ENDPOINTS

Objectives	Endpoints
Primary	
To characterize the PK profile of donanemab following administration of 350 mg intravenous (IV) doses in healthy participantsArea under the concentration versus time curve 0 to 4 weeks (AUC_{0-4 weeks})Maximum observed drug concentration during a dosing interval at steady state (C_{max, ss}) andArea under the concentration versus time curve during a dosing interval at steady state (AUC_{T, ss})
Secondary	
To investigate the safety and tolerability of donanemab following administration of 350 mg IV doses in healthy participantsIncidence of treatment-emergent adverse events (TEAE) and serious adverse events (SAE).
Exploratory	
To assess the effect of treatment-emergent anti-drug antibodies (TE-ADAs) on the PK of 350 mg IV donanemabModel parameters for the exposure-response relationship between donanemab serum concentrations and anti-drug antibody (ADA) titerTo characterize immunogenicity of donanemab following administration of 350 mg IV doses in healthy participantsIncidence of TE-ADA

5. STUDY DESIGN

This is a Phase 1, open-label study to evaluate the PK, safety, and tolerability of 350 mg donanemab administered as a single IV dose every 2 weeks (Q2W) for 10 weeks in healthy participants. Approximately 40 participants may be enrolled so that approximately 25 participants complete the study. Participants will receive a single 350 mg dose of donanemab Q2W for 10 weeks. After each dose administration, participants will remain in the clinical research unit (CRU) for up to 5 days. Participants will return to the CRU for regular outpatient visits until the next dose of donanemab. These visits will occur on Days 3, 4, 5, and 8 (unless the participant is still admitted to the CRU, in which activities for those days will be performed during the inpatient stay). After the last dose of donanemab, participants will return for outpatient visits up to 12 weeks after the last dose.

Screening may occur up to 28 days prior to enrollment into the study. Once the informed consent is signed by the participants, they will be assessed for eligibility and will undergo screening procedures.

[figure not shown]
Participants who are not enrolled within 28 days of screening may undergo an additional medical assessment and/or clinical measurements to confirm their eligibility. Eligible participants will be admitted to the CRU on Day -1 prior to dosing in each of the 6 treatment periods. On Day 1 of

each treatment period, participants will be dosed with an IV dose of donanemab and remain in the CRU until discharge on Day 2, although participants may remain inpatient up to Day 5 of each treatment period at the discretion of the investigator. After dosing with 350 mg donanemab, participants will return to the CRU approximately 2 weeks later to be admitted at Day -1 of the subsequent period.

Safety and tolerability will be assessed through electrocardiograms (ECGs), clinical laboratory tests, vital sign measurements, recording of adverse events (AEs), physical examination, and neurological examination. Additionally, immunogenicity will be assessed.

After discharge from the CRU after the final treatment period, participants will return for further outpatient assessments (safety, PK, and immunogenicity) until 12 weeks after the final dose.

Study Schema

Abbreviations: CRU = Clinical research unit

Figure 1: Illustration of Study Design for Protocol I5T-MC-AACP

6. BLINDING

This is a non-randomized, open-label study.

7. TREATMENT

The following shows the study treatment abbreviation that will be used in the TFLs.

Study Treatment Name	Treatment order in TFL
350 mg donanemab Q2W	1

Abbreviations: Q2W = every 2 weeks

8. SAMPLE SIZE JUSTIFICATION

Approximately 40 participants may be enrolled so that approximately 25 participants complete the study. The sample sizes described are customary for Phase 1 studies evaluating safety, PK, and immunogenicity and is not powered on the basis of statistical hypothesis testing.

9. DEFINITION OF ANALYSIS POPULATIONS

The “Entered” population will consist of all participants who sign the informed consent form.

The “Enrolled” population will consist of all enrolled participants.

The “Safety” population will consist of all participants randomly assigned to study intervention and who take at least 1 dose of study donanemab. Participants will be analyzed according to the amount of intervention they actually received.

The “Pharmacokinetic” population will consist of all enrolled participants who received at least 1 full dose of donanemab and have baseline and at least one post-baseline evaluable PK sample. Participants will be analyzed according to the amount of intervention they actually received.

All protocol deviations that occur during the study will be considered for their severity/impact and will be taken into consideration when participants are assigned to analysis populations.

10. STATISTICAL METHODOLOGY

10.1 General

Data listings will be provided for all data that is databased. Summary statistics and statistical analysis will only be presented for data where detailed in this SAP. For continuous data, summary statistics will include the arithmetic mean, arithmetic standard deviation (SD), median, minimum, maximum and number of observations; for log-normal data (e.g. the PK parameters: area under the concentration versus time curve [AUCs] and maximum observed drug concentration [C_{max}]) the geometric mean and geometric coefficient of variation (CV%) will also be presented. For categorical data, frequency count and percentages will be presented. Data listings will be provided for all participants up to the point of withdrawal, with any participants excluded from the relevant population highlighted. Summary statistics and statistical analyses will generally only be performed for participants included in the relevant analysis population. For the calculation of summary statistics and statistical analysis, unrounded data will be used.

For change from baseline summary statistics, each individual change from baseline will be calculated by subtracting the individual participant’s baseline value from the value at that time point. The individual participants’ change from baseline values will be used to calculate the summary statistics (arithmetic mean, arithmetic SD, median, minimum, maximum and number of observations) using a SAS procedure such as Proc Univariate.

Data analysis will be performed using SAS® Version 9.4 or greater.

10.2 Demographics and Participant Disposition

Participant disposition will be summarized and listed. The demographic variables age, sex, race, ethnicity, country of enrolment, site ID, body weight, height and body mass index will be summarized and listed. All other demographic variables will be listed only.

10.3 Pharmacokinetic Assessment

10.3.1 Pharmacokinetic Analysis

Noncompartmental methods applied with a validated software program (WinNonlin Phoenix v8.3.5 or higher) to the serum concentrations of LY3002813 (donanemab), will be used to determine the following PK parameters, when possible:

Serum Pharmacokinetic Parameters of LY3002813 (Donanemab):

Parameter	Units	Definition
AUC _{0-4weeks}	ug*h/m L	area under the concentration versus time curve from time 0 to 4weeks (Month 1, 2 and 3) ^a
AUC _{0-2weeks}	ug*h/m L	area under the concentration versus time curve for first dosing interval (Treatment Period 1 to 6)
AUC _{τ,ss}	ug*h/mL	area under the concentration versus time curve during one dosing interval at steady state (Treatment Period 6)
AUC(0-t _{last})	ug*h/mL	area under the concentration versus time curve from time zero to time t, where t is the last time point with a measurable concentration (Treatment Periods 1 to 6)
AUC (0-∞)	ug*h/mL	area under the concentration versus time curve from zero to infinity (only after 1 st dose and after last dose on Day 71)
%AUC(t _{last} -∞)		Percentage of AUC(0-∞) extrapolated
C _{max,ss}	ug/mL	maximum observed drug concentration during a dosing interval at steady state (Treatment Period 6)
C _{max}	ug/mL	maximum observed drug concentration (Treatment Periods 1 to 5)
C _{min}	ug/mL	minimum observed drug concentration during a dosing interval at steady state (Treatment Period 1 to 5)
C _{min,ss}	ug/mL	minimum observed drug concentration during a dosing interval at steady state (Treatment Period 6)
t _{1/2}	days	half-life associated with the terminal rate constant ($λz$) in non-compartmental analysis (Treatment Period 6)
t _{max}	days	time to maximum observed drug concentration (Treatment Period 1 to 5)
t _{max,ss}	days	time to maximum observed drug concentration at steady state (Treatment Period 6)
CL _{ss}	L/h	total body clearance of drug calculated at steady state after intravenous administration (Treatment Period 6)

V_{ss}	L	volume of distribution at steady state following intravenous administration (Treatment Period 6)
RA_{AUC}		accumulation ratio for $AUC_{t,ss}$ at steady state / $AUC_{0-2\text{weeks}}^b$
$RA_{C_{max}}$		accumulation ratio for $C_{max,ss}$ at steady state / $C_{max, \text{day 1}}$ ^b

^a Parameter will be calculated as the sum of $AUC_{0-2\text{weeks}}$ for treatment periods 1 and 2 (Month 1), periods 3 and 4 (Month 2) and periods 5 and 6 (Month 3).

^b $AUC_{t,ss}$ and $C_{max,ss}$ based on Period 6; $AUC_{0-2\text{weeks}}$ and C_{max} values based on Period 1

Additional PK parameters may be calculated, as appropriate.

The software and version used for the final analyses will be specified in the CSR. Any exceptions or special handling of data will be clearly documented within the final CSR. Formatting of tables, figures and abbreviations will follow the Eli Lilly Global PK/PD/TS Tool: NON-COMPARTMENTAL PHARMACOKINETIC STYLE GUIDE. The version of the tool effective at the time of PK analysis will be followed.

General PK Parameter Rules

- Actual sampling times will be used in the final analyses of individual PK parameters, except for non-bolus pre-dose sampling times which will be set to zero. For non-bolus, multiple dose profiles, the pre-dose time will be set to zero unless a time deviation falls outside of the protocol blood collection time window which is considered to impact PK parameter derivation.
- C_{max} will be reported from observed values.
- AUC parameters will be calculated using a combination of the linear and logarithmic trapezoidal methods (linear-log trapezoidal rule). The linear trapezoidal method will be applied up to t_{max} and then the logarithmic trapezoidal method will be used after t_{max} . The minimum requirement for the calculation of AUC will be the inclusion of at least three consecutive plasma concentrations above the lower limit of quantification, with at least one of these concentrations following C_{max} . $AUC(0-\infty)$ values where the percentage of the total area extrapolated is more than 20% will be flagged. Any $AUC(0-\infty)$ value excluded from summary statistics will be noted in the footnote of the summary table.
- Half-life ($t_{1/2}$) will be calculated, when appropriate, based on the apparent terminal log-linear portion of the concentration-time curve. The start of the terminal elimination phase for each participant will be defined by visual inspection and generally will be the first point at which there is no systematic deviation from the log-linear decline in plasma concentrations. Half-life will only be calculated when a reliable estimate for this parameter can be obtained comprising of at least 3 data points. If $t_{1/2}$ is estimated over a time window of less than 2 half-lives, the values will be flagged in the data listings. Any $t_{1/2}$ value excluded from summary statistics will be documented in the footnote of the summary table.

- A uniform weighting scheme will be used in the regression analysis of the terminal log-linear portion of the concentration-time curve.
- The parameters based on predicted C_{last} will be reported.

Individual PK Parameter Rules

- Only quantifiable concentrations will be used to calculate PK Parameters with the exception of special handling of certain concentrations reported below the lower limit of quantitation (BQL). Plasma concentrations reported as BQL will be set to a value of zero when all of the following conditions are met:
 - The compound is non-endogenous.
 - The samples are from the initial dose period for a participant or from a subsequent dose period following a suitable wash-out period.
 - The time points occur before the first quantifiable concentration.
- All other BQL concentrations that do not meet the above criteria will be set to missing.
- Also, where two or more consecutive concentrations are BQL towards the end of a profile, the profile will be deemed to have terminated and therefore any further quantifiable concentrations will be set to missing for the calculation of the PK parameters unless it is considered to be a true characteristic of the profile of the drug.

For multiple-dosing data, when pre-dose concentrations are missing, the value to be substituted will be C_{min} for the dosing interval.

Individual Concentration vs. Time Profiles

- Individual concentrations will be plotted utilizing actual sampling times.
- The terminal point selections will be indicated on a semi-logarithmic plot.

Average Concentration vs. Time Profiles

- The average concentration profiles will be graphed using scheduled (nominal) sampling times.
- The average concentration profiles will be graphed using arithmetic average concentrations.
- The pre-dose average concentration for single-dose data from non-endogenous compounds will be set to zero. Otherwise, only quantifiable concentrations will be used to calculate average concentrations.

- Concentrations at a sampling time exceeding the sampling time window specified in the protocol, or $\pm 10\%$, will be excluded from the average concentration profiles.
- Concentrations excluded from the mean calculation will be documented in the final study report.
- A concentration average will be plotted for a given sampling time only if 2/3 of the individual data at the time point have quantifiable measurements that are within the sampling time window specified in the protocol or $\pm 10\%$. An average concentration estimated with less than 2/3 but more than 3 data points may be displayed on the mean concentration plot if determined to be appropriate and will be documented within the final study report.

Treatment of Outliers during Pharmacokinetic Analysis

Application of this procedure to all PK analyses is not a requirement. Rather, this procedure provides justification for exclusion of data when scientifically appropriate. This procedure describes the methodology for identifying an individual value as an outlier for potential exclusion, but does not require that the value be excluded from analysis. The following methodology will not be used to exclude complete profiles from analysis.

Data within an Individual Profile

A value within an individual profile may be excluded from analysis if any of the following criteria are met:

- For PK profiles during multiple dosing, the concentration of the pre-dose sample exceeds all measured concentrations for that individual in the subsequent post-dose samples.
- For PK profiles during single dosing of non-endogenous compounds, the concentration in a pre-dose sample is quantifiable.
- For any questionable datum that does not satisfy the above criteria, the profile will be evaluated and results reported with and without the suspected datum.

Data between Individual Profiles

1. If $n \geq 6$, then an objective outlier test will be used to compare the atypical value to other values included in that calculation:
 - a. Transform all values in the calculation to the logarithmic domain.
 - b. Find the most extreme value from the arithmetic mean of the log transformed values and exclude that value from the dataset.
 - c. Calculate the lower and upper bounds of the range defined by the arithmetic mean $\pm 3 \times SD$ of the remaining log-transformed values.

- d. If the extreme value is within the range of arithmetic mean $\pm 3*SD$, then it is not an outlier and will be retained in the dataset.
- e. If the extreme value is outside the range of arithmetic mean $\pm 3*SD$, then it is an outlier and will be excluded from analysis.

If the remaining dataset contains another atypical datum suspected to be an outlier and $n \geq 6$ following the exclusion, then repeat step 1 above. This evaluation may be repeated as many times as necessary, excluding only one suspected outlier in each iteration, until all data remaining in the dataset fall within the range of arithmetic mean $\pm 3*SD$ of the log-transformed values.

Reporting of Excluded Values

Individual values excluded as outliers will be documented in the final CSR. Approval of the final CSR will connote approval of the exclusion.

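### SAP 10.3.1 defines Cmin for Periods 1–5 as a steady-state interval minimum, so a literal reading gives 0 in Period 1 and normally the preceding trough in Periods 2–5

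*SAP*

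**What the plan says.** The parameter table in SAP 10.3.1 gives Cmin for the first five periods as "minimum observed drug concentration during a dosing interval at steady state (Treatment Period 1 to 5"), and Cmin,ss as "minimum observed drug concentration during a dosing interval at steady state (Treatment Period 6"). The two definitions differ only in the period. The footnote to the same table takes the steady-state AUC and Cmax from Period 6 and the first-dose reference for the accumulation ratios from Period 1.

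Three further rules in 10.3.1 bear on the result:
- Time zero: "For non-bolus, multiple dose profiles, the pre-dose time will be set to zero unless a time deviation falls outside" the collection window. The pre-dose sample is therefore the first point of its own period's profile.
- Values below quantification (BQL): "Plasma concentrations reported as BQL will be set to a value of zero when all of the following conditions are met". The conditions are that the compound is non-endogenous, that "The samples are from the initial dose period for a participant or from a subsequent dose period following a suitable wash-out period", and that "The time points occur before the first quantifiable concentration".
- Missing pre-dose: "when pre-dose concentrations are missing, the value to be substituted will be" the Cmin of the dosing interval.

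No rule keeps the pre-dose sample out of Cmin, and none says whether the next period's pre-dose sample closes the interval. The Schedule of Activities (protocol 1.3) places PK samples in each period on Day -1, pre-dose, at end of infusion, at 24, 48, 72 and 96 hours, and on Day 8. After Period 6 there are two more, on Days 37 and 96.

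**The concern.** While drug accumulates, the concentration just before a dose is lower than the concentration 14 days after it. The interval minimum is then the starting value, which belongs to the preceding interval. Period 1 starts from no drug, so its minimum is zero and says nothing about the trough that the first dose leaves. A reader of a Cmin-by-period table would take each entry as that period's trough, whereas the series would start at zero and run one period late.

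The substitution rule rests on the same steady-state premise. Start and end of an interval are interchangeable only at steady state. The rule is also circular: Cmin normally is the pre-dose value, so once that value is missing, Cmin comes from a later sample and means something different in that participant.

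**Working it through.** **Sample count.** The plan states no Cmin value, but its sample count confirms what each period contains: 6 periods × 8 samples + Day 37 + Day 96 = 50, and 50 × 4 mL = 200 mL. Both match protocol 10.2.1. Within a period, nothing is sampled after Day 8. An observed end-of-interval value can come only from the next period's Day -1 or pre-dose sample.

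**Period 1, from the rules alone.** Exclusion criterion 24 removes anyone who took part in an earlier donanemab study, so the pre-dose sample is expected to be BQL. It belongs to the initial period, precedes the first quantifiable value, and the compound is a non-endogenous antibody. It is set to 0 at time zero, and the interval minimum is 0.

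**Periods 2–5, by superposition.** Inputs: interval 14 days; half-life h of about 4.7 days (at or below 3 mg/kg) and 11 days (10 to 40 mg/kg), both from protocol 4.3. Assumptions: one compartment, constant clearance, unit rise per dose.

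Let e = 2^(−14/h), which is 0.127 (4.7 d) or 0.414 (11 d). The end trough of period n is T_n = e + e² + … + eⁿ, and the pre-dose value of period n is T_(n−1).

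| Period | Pre-dose / end trough, 4.7 d | Ratio | Pre-dose / end trough, 11 d | Ratio |
|---|---|---|---|---|
| 1 | 0 / 0.127 | 0 | 0 / 0.414 | 0 |
| 2 | 0.127 / 0.143 | 0.887 | 0.414 / 0.585 | 0.707 |
| 3 | 0.143 / 0.145 | 0.986 | 0.585 / 0.656 | 0.892 |
| 4 | 0.145 / 0.145 | 0.998 | 0.656 / 0.685 | 0.957 |
| 5 | 0.145 / 0.145 | 1.000 | 0.685 / 0.698 | 0.983 |

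The gap, 1 − ratio, is 11–29% in Period 2, 1–11% in Period 3 and under 5% in Periods 4–5.

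**When the end trough is the minimum instead.** If the next pre-dose sample counts and the half-life in period n falls to h′, the end trough is lower when (T_(n−1) + 1) × 2^(−14/h′) < T_(n−1). In Period 2 this gives h′ < 7.90 days from 11 (clearance up 39%), or h′ < 4.44 days from 4.7 (up about 6%). Later thresholds are 13%, 5% and 2% from 11 days, and under 1% from 4.7 days.

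**Missing pre-dose in Period 2.**
- Next pre-dose sample counts: the substitute is T_2, and T_2/T_1 = 1 + e = 1.13 (4.7 d) or 1.41 (11 d).
- Only samples to Day 8 count: the substitute is the value 7 days after the dose, (T_1 + 1) × 2^(−7/h) = 0.401 (4.7 d) or 0.910 (11 d). Divided by T_1, this is 3.2 or 2.2.

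**Effect on AUC.** In its own profile the substitute touches only the stretch from pre-dose to end of infusion. Taking 30 minutes (the minimum in protocol 6.1.1) and the Day 8 substitute at 11 days, the added area is ½ × 0.5 h × (0.910 − 0.414) = 0.124. The Period 2 AUC is 1.414 × 0.586 × (11/0.693) × 24 = about 316, so the change is 0.04%.

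**The case against.** Cmin is not a primary, secondary or exploratory endpoint. Accumulation is measured by RA_AUC and RA_Cmax, and SAP 10.4.7 plots an observed C_trough on Days 15, 29, 43, 57 and 71. Those days are the ends of Periods 1–5. Concentrations are also listed and profiles plotted. This stands: a reader might infer that the approach to steady state is hidden, or that the Period 6 primary parameters are compromised, and the documents support neither. C_trough is, however, left undefined and is shown only against ADA titer, so it does not replace a by-period Cmin table.

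The percentages can also be read as errors. They are not errors against the SAP's own definition: if the pre-dose value is lowest, it is the interval minimum. They measure how far that minimum lies from the trough a reader would expect.

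Nor is it certain that Cmin in Periods 2–5 repeats the preceding trough. Protocol 4.3 leaves linearity at 350 mg open, and protocol 2.2 reports TE-ADA in 92.2% of patients, which could raise clearance. If the next pre-dose sample counts, modest rises make the period's own end trough the minimum. Period 1 does not depend on this.

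An analyst may leave out the pre-dose sample by convention, but the SAP does not say so. A zero has no geometric mean, but 10.1 names only AUCs and Cmax as examples for geometric summaries, so that consequence is conditional.

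**Conclusion.** The point holds as a minor defect of definition. The steady-state wording is wrong for Periods 1–5 on the SAP's own terms, since Period 1 cannot be both the first-dose reference and a steady-state interval. The Period 1 value of 0 follows from the stated rules and needs no model. The figures for Periods 2–5 and for the substitution rule rest on one-compartment kinetics, constant clearance and the two half-lives in the protocol. The two substitution ranges also depend on which samples are taken to close the interval, which the SAP leaves open. The consequence is a misleading descriptive table in Periods 1–3 and little difference in Periods 4–5. It does not reach the conclusions drawn from the primary AUC and Cmax parameters.

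**What to change.** In SAP 10.3.1:
1. Remove the steady-state wording from the Periods 1–5 row. Define the parameter as the end-of-interval trough: the next period's pre-dose sample, or its Day -1 sample if that is missing. Use the same definition for C_trough in 10.4.7.
2. State that Period 6 has no observed end-of-interval sample, because nothing is drawn between Day 8 and Day 37. Choose one definition for Cmin,ss: the Period 6 pre-dose value, labelled as the same sample as the Period 5 trough, or a 14-day value interpolated log-linearly between Day 8 and Day 37.
3. Replace the missing pre-dose rule: zero in Period 1; otherwise the same period's Day -1 value, extrapolated log-linearly to dosing time. If Day -1 is about one day earlier, carrying it forward unchanged would be 2^(1/11) = 1.07 to 2^(1/4.7) = 1.16 times the true value.

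The cost is SAP wording. Every sample named is already scheduled.
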